9.2 Setting

The study population will include all individuals registered in the databases receiving CPA/EE (ATC G03HB01) and Gemscript codes (85864998, 86466998, 86925998, 87351998, 90826979, 91068998, 91069998, 94832990, 94913992, 94920998, 95396990, 96577998 and 97520998) between January 1, 2011 and December 31, 2012 (study period for the first run) or January 1, 2014 and December 31, 2014 (study period for the second run). The year 2013 is not included in the identification period, as this is the year in which changes in policies and recommendations for CPA/EE usage have been implemented. The date of receiving the first prescription of CPA/EE in the study period will be defined as the index date.

The annual study periods for the 2017 extension will be between January 1 and December 31 of 2015, 2016 and 2017, respectively.

Exclusion criteria are:

- Men
- <365 days recorded history in the database prior to index date
- Use of CPA/EE in the year prior to the index date, defined by
 - a prescription of CPA/EE in the year prior to index date, or
 - a prescription of CPA/EE in the year prior to entry date (start of the study period or database entry, whichever occurred first) (THIN only, see Table 5.1 deviation #3) or
 - expiration of a prescription of CPA/EE in the year prior to index date (PHARMO only, see Table 5.1 deviation #1)

Patients will be followed from index date to transfer out of the database (end of follow-up available/censoring), end of study period, whichever occurs first. The first run will include an overall analysis (2011-2012) and an analysis by calendar year (2011 and 2012), for which separate recruitments will be performed (i.e. summing patients from the analysis by calendar year 2011 and 2012 may give a higher number than for the overall analysis). In the analysis by calendar year the end of the study period will be defined as December 31 of the year of index date (December 31, 2011, December 31, 2012).

For the 2017 study extension an analysis by calendar years will be performed..

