9.3.1 Episodes of CPA/EE and hormonal contraceptive use

The duration of each CPA/EE and hormonal contraceptive prescription will include the medication-free days, if applicable. For CPA/EE, which is dosed in cycles of 21 days on medication and a 7-day interval without medication, the duration of one blister pack will thus be 28 days and the duration of a prescription will be the duration of one blister pack * the number of blister packs prescribed (see Figure 9.1). Most (if not all) oral hormonal contraceptives, patches and rings are also dosed in 28-day cycles with variations in the number of medication-free days. For intra-uterine devices, injections and implants the duration will be defined as the duration of effectiveness or until removal of the intra-uterine devices or implant when this is identified in the database. For each hormonal contraceptive the duration of effectiveness will be defined from the label.

Subsequent prescriptions of the same drug will be concatenated if the new prescription date precedes the end date of the previous prescription. The adjusted start date of the new prescription will be the day after the end date of the previous prescription. Subsequently, prescriptions of CPA/EE and hormonal contraceptives between index date – 365 days and end of follow-up will be converted into treatment episodes of uninterrupted use. In case of an interruption between two prescriptions, use of the drug will be considered interrupted and the treatment episode ends, i.e. no gap is allowed between two prescriptions.

Patients may have several treatment episodes of CPA/EE and hormonal contraceptives after treatment onset.

[figure not shown]

Figure 9.1 Cycles, prescriptions and treatment episodes of CPA/EE and hormonal contraceptives

Each box indicates one cycle, e.g. a blister pack. Subsequent cycles constitute a prescription, and subsequent prescriptions constitute a treatment episode.

9.3.2 Definition of switching and (potential) concomitant use of CPA/EE and hormonal contraceptives

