Switching between hormonal contraceptives will be defined as a prescription date of a new hormonal contraceptive preceding the end date of a previous episode of another hormonal contraceptive. As most hormonal contraceptives are given in cycles, the assumption will be that the user will finish a cycle (e.g. the blister pack or patch) of the first hormonal contraceptive before starting a new one. Hence, the adjusted end date of the previous episode will be the end date of the cycle during which the new prescription was observed. The adjusted start date of the new hormonal contraceptive will be the day after the adjusted end date of the previous.

If the previous contraceptive is not given in cycles (e.g. progestogen-only pills, intra-uterine devices, implants) the adjusted end date will be the day before the date of the new prescription and the start date of the new hormonal contraceptive will not be adjusted.

For all episodes of CPA/EE, overlap with hormonal contraceptive episodes will be assessed similarly to the switches between hormonal contraceptives. However, as concomitant use of CPA/EE and hormonal contraceptives is among the study objectives, we will not define a switch but classify in terms of (potential) concomitant use. The days between the adjusted end date and the original end date of a truncated episode will be classified as:

- Potential concomitant use: (see Figure 9.2) when a “switch” from CPA/EE to a hormonal contraceptive *or vice versa* occurs during the last prescription within a treatment episode
- Concomitant use: when both start and end date of a hormonal contraceptive episode lie between start and end date of a CPA/EE episode *or vice versa*; or when a “switch” from CPA/EE to a hormonal contraceptive *or vice versa* precedes the last prescription within a treatment episode.
- Non-concomitant use: both start and end date of a hormonal contraceptive episode lie outside a CPA/EE episode (i.e. before or after both start and end date of a CPA/EE episode).
- No use of hormonal contraceptives (no observed treatment episodes of hormonal contraceptives within 365 days before the index date until end of follow-up).

Because the validity of estimating duration differs between administration routes (oral, intra-uterine, implant, injection, ring and patch) concomitant use will be computed separately and presented separately in text or tables, depending on the numbers observed.

[figure not shown]

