15.2 Concomitant use of hormonal contraceptives

15.2.1 Concomitant use of hormonal contraceptives in PHARMO

Table 15.4 Concomitant use of other HC among new CPA/EE users in PHARMO per calendar year

| | 2011 starters N=0,000 n (%) | 2012 starters N=0,000 n (%) | 2014 starters N=0,000 (%) | 2015 starters N=0,000 n (%) | 2016 starters N=0,000 n (%) | 2017 starters N=0,000 n (%) |
|---|--------------------------------------|--------------------------------------|------------------------------------|--------------------------------------|--------------------------------------|--------------------------------------|
| Number of CPA/EE episodes during follow-up 1 2 ≥3 mean ± SD median (IQR) Summed duration of CPA/EE use (months) ¹⁾ 0-3 4-6 7-12 mean ± SD median (IQR) | | | | | | |
| Concomitant use Concomitant and potential concomitant use ²⁾ Potential concomitant use Non-concomitant use No use of other HC Duration of concomitant use of other HC ≤28 days >28 - 84 days >84 days mean ± SD median (IQR) Duration of potential concomitant use of other HC (days) ≤28 days >28 - 84 days >84 days mean ± SD median (IQR) | | | | | | |

1) by definition, the follow-up and thus summed duration of use will not be longer than 12 months (see section 9.2).

2) A user may be concomitant and potential concomitant user at different times during CPA/EE use.

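### In the calendar-year analyses, overlap that starts in the last prescription visible before 31 December is classed as concomitant or potential by the data cut, not by whether that prescription was renewed

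*Protocol*

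**What the plan says.** Section 9.2 closes follow-up for each yearly cohort at the calendar year end: "In the analysis by calendar year the end of the study period will be defined as December 31 of the year of index date". The extension follows the same pattern: "The annual study periods for the 2017 extension will be between January 1 and December 31 of 2015, 2016 and 2017, respectively".

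Section 9.3.1 limits the prescriptions that are read: "prescriptions of CPA/EE and hormonal contraceptives between index date – 365 days and end of follow-up will be converted into treatment episodes". Section 9.3 sets the same upper limit.

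Section 9.3.2 then classifies overlap between CPA/EE and a hormonal contraceptive (HC):

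- It is potential concomitant use when the switch "occurs during the last prescription within a treatment episode".
- It is concomitant use when the switch "precedes the last prescription within a treatment episode", or when one episode is nested in the other: "when both start and end date of a hormonal contraceptive episode lie between start and end date of a CPA/EE episode", or the reverse.
- The woman is assumed to finish the cycle in progress. Only the days from the adjusted to the original end date of the truncated episode are classified.

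A footnote to Tables 15.4 to 15.6 adds: "by definition, the follow-up and thus summed duration of use will not be longer than 12 months". The protocol does not say whether a supply running past 31 December has its end date cut to that day. It provides no look-ahead, and section 9.9 does not list the effect as a limitation.

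**The concern.** Whether a prescription is the last of its episode depends on whether it was renewed. For a woman still in treatment on 31 December, the deciding renewal falls in January and is not read. The final visible prescription then counts as last because of the calendar. The class of any overlap that starts in it reflects the cut and not her refill behaviour.

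This matters because section 7 names concomitant use as the exposure that may raise thromboembolic risk, and section 8.2 makes its trend an objective. Tables 15.4 to 15.6 report concomitant and potential use on separate rows with separate durations, so an artefact that moves women between those rows touches the main result of the extension.

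**Working it through.** **1. Reproduce the stated follow-up.** With index dates uniform over the year and censoring at 31 December, follow-up is uniform on 0 to 12 months. The mean is 6, the SD is 12/√12 = 3.5, the quartiles are 3 and 9, and 50% have under 6 months. Tables 15.1 to 15.3 give 6 ± 3 or 6 ± 4 months and a median (IQR) of 6 (3-9) in eight of nine completed columns (HSD 2014: 7 (3-10)). The shares under 6 months run from 118/261 = 45% (HSD 2014) to 224/446 = 50% (HSD 2012). The model fits.

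**2. Inputs not in the protocol.** Section 9.3.1 fixes a 28-day pack but not the packs per prescription. I take 1, 3 or 6 packs, so L = 28, 84 or 168 days. Continuous CPA/EE use, on-time refills and a constant rate of HC starts are also assumed, as is dual use that truly continues into January.

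**3. Person-time in the final visible prescription.** For follow-up t uniform on 0 to 365 days, the time since the last refill is t − L·floor(t/L). Its share of person-time is [n·L²/2 + r²/2] / (365²/2), with n = floor(365/L) and r = 365 − nL. The denominator is 66,612.5. The cycle running on 31 December is the L = 28 case, 7.65%.

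| L (days) | n | r | Numerator | Share | Less running cycle |
|---|---|---|---|---|---|
| 28 | 13 | 1 | 5,096.5 | 7.65% | 0% |
| 84 | 4 | 29 | 14,532.5 | 21.8% | 14.2% |
| 168 | 2 | 29 | 28,644.5 | 43.0% | 35.4% |

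The last column is needed because of the cycle rule. An HC started in the cycle running on 31 December produces no classifiable day before the cut. For example, CPA/EE for 84 days from 10 November runs to 1 February, with cycles ending 7 December, 4 January and 1 February. An HC prescribed on 10 December gives an adjusted end of 4 January, so the classifiable days are 5 January to 1 February, all outside follow-up.

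**4. A case with days inside follow-up (constructed dates).** CPA/EE for 84 days from 15 October runs to 6 January, with cycles ending 11 November, 9 December and 6 January. An 84-day HC is prescribed on 1 November. The adjusted CPA/EE end is 11 November, and the HC runs from 12 November to 3 February. Classifiable days within follow-up are 12 November to 31 December: 19 + 31 = 50.

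- End dates not cut, January not read: the switch is in the last visible CPA/EE prescription and the HC ends after it, so the overlap is potential.
- Same woman, CPA/EE renewal on 7 January read: the switch precedes the last prescription, so the overlap is concomitant.
- End dates cut: both episodes end on 31 December. If a shared end date counts as lying within, the nesting rule gives concomitant, whether or not CPA/EE was renewed.

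**5. Mirror case.** An HC already running at index has residual supply uniform on 0 to L and is renewed later. The chance that renewal falls after the cut is (L/2)/365 = L/730, which is 3.8%, 11.5% and 23.0%.

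**6. Sensitivity.** With one uniformly timed HC start per woman instead of a constant rate, simulation gives 17%, 38% and 60% before excluding the running cycle. The 24-month 2011-2012 window gives about 4%, 11% and 22% by person-time, roughly half the yearly figures. Reading one further prescription length beyond 31 December, for classification only, brings the artefact to 0% in this model.

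**The case against.** The strongest reply is that the rule is reasonable: where no renewal has been seen, calling the overlap potential is a fair description. The tables also show concomitant, both, and potential use on separate rows, so total overlap can be recovered. That stands for the total. It does not help the split between rows, which the tables are designed to report.

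A reader might infer three stronger things that the documents do not support:

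- *That all concomitant use running into January is downgraded.* It is not. Overlap that began before the final prescription stays concomitant, as does a nested episode. If a refill is issued before 31 December, the earlier prescription is no longer the last.
- *That reported concomitant use is biased downward.* This requires end dates that are not cut. The footnote tying duration of use to follow-up suggests they may be, and the error could then run the other way.
- *That the trend is distorted.* Every yearly cohort has the same cut, follow-up is stable across the nine completed columns, and nothing in the protocol shows prescription length changing.

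A further objection concerns the remedy. Table 5.1 (item 6) records the regulator's request for unchanged methodology and presentation, so replacing the classification in all years would conflict with it. That objection is sound and shapes the fix.

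**Conclusion.** The point holds in a limited form. For women still in treatment at year end, overlap that starts in the final visible prescription is classified by the data cut, and the protocol leaves open which way the error goes. The CPA/EE person-time exposed to this is about 8%, 22% and 43% at 28, 84 and 168 days per prescription, or about 0%, 14% and 35% where overlap could also be counted before the cut. With single-pack prescriptions the countable effect in this case vanishes; with multi-pack prescriptions it does not.

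These are shares of person-time under the assumptions in the working, not percentage points of the reported proportion of concomitant users. That effect cannot be computed, because the concomitant-use rows of Tables 15.4 to 15.6 are empty shells. The consequence is for the level and the concomitant/potential split. The trend is touched only if prescription length or the timing of starts shifts over the years.

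**What to change.** In 9.3.1 and 9.3.2:

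- State whether supply end dates are cut at 31 December and, if so, whether a shared end date satisfies the nesting rule.
- Keep 31 December as the limit for counting overlap days.
- For every calendar-year cohort, keep the present classification in Tables 15.4 to 15.6 and add a second version beside it. In that version, prescriptions dated after 31 December, up to the supply end of the prescription running on that day, are read only to decide whether it was the last of its episode.
- Flag the 2017 cohort if early-2018 records are not in the mid-2018 extract.

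Showing both versions preserves comparability with the earlier report, and a gap in early-2018 data would not break the existing series. The cost is a slightly wider extraction and extra programming in three databases. No new patients or data sources are needed.

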8.2 Additional objectives

An additional study objectives added are to assess among new users of CPA/EE in 2015, 2016 and 2017:

- Patient demographics
- (Concomitant) use of hormonal contraceptives
- to assess trends in concomitant use over 2011-2017 (excluding 2013)

9. Research methods

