9.7 Data analysis

Patient, treatment and diagnosis characteristics will be reported descriptively. Categorical data will be presented as counts (n) and proportions (%). Continuous data will be presented as means with standard deviation (SD) and as medians with inter quartile range (IQR) when appropriate. Results will be stratified by year of index date. Table shells are presented in Annexes 1 and 2 (sections 14 and 15).

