15.1 Patient selection and characteristics

15.1.1 Patient selection and characteristics in PHARMO

[figure not shown]

Figure 15.1 Flow chart of patient selection in PHARMO

NOTE: this flow chart will be repeated for each database. An additional level of ‘GP data available’ will be added for PHARMO

Table 15.1 General characteristics of new CPA/EE users in PHARMO per calendar year

| | 2011 starters N=7,876 n (%) | 2012 starters N=7,562 n (%) | 2014 starters N=1,401 n (%) | 2015 starters N=0,000 n (%) | 2016 starters N=0,000 n (%) | 2017 starters N=0,000 n (%) |
|---|--|--|--|--|--|--|
| Age (years) | | | | | | |
| <15 | 278 (4) | 262 (3) | 13 (1) | | | |
| 15-<25 | 3,986 (51) | 3,733 (49) | 482 (34) | | | |
| 25-<35 | 2,385 (30) | 2,365 (31) | 584 (42) | | | |
| 35-<45 | 1,001 (13) | 968 (13) | 242 (17) | | | |
| 45-<55 | 211 (3) | 229 (3) | 73 (5) | | | |
| ≥55 | 15 (<0.5) | 5 (<0.5) | 7 (<0.5) | | | |
| mean ± SD | 25 ± 9 | 25 ± 9 | 29 ± 9 | | | |
| median (IQR) | 23 (18-31) | 24 (18-31) | 27 (23-34) | | | |
| Database history before index date (years) | | | | | | |
| 1-<2 | 420 (5) | 418 (6) | 91 (6) | | | |
| 2-4 | 966 (12) | 648 (9) | 140 (10) | | | |
| >4 | 6,490(82) | 6,496 (86) | 1,170 (84) | | | |
| mean ± SD | 8 ± 4 | 9 ± 4 | 9 ± 5 | | | |
| median (IQR) | 7 (5-12) | 8 (6-13) | 9 (6-11) | | | |
| Follow-up after index date (months)* | | | | | | |
| <6 | 3,877 (49) | 3,573 (47) | 641 (46) | | | |
| 6-12 | 3,999 (51) | 3,989 (53) | 760 (54) | | | |
| mean ± SD | 6 ± 3 | 6 ± 3 | 6 ± 3 | | | |
| median (IQR) | 6 (3-9) | 6 (3-9) | 6 (3-9) | | | |

* by definition, the follow-up will not be longer than 12 months (see section 9.2).

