15.1.2 Patient selection and characteristics in THIN

[figure not shown]

Figure 15.2 Flow chart of patient selection in THIN

Table 15.2 General characteristics of new CPA/EE users in THIN per calendar year

| | 2011 starters N=2,760 n (%) | 2012 starters N=2,923 n (%) | 2014 starters N=2,341 n (%) | 2015 starters N=0,000 n (%) | 2016 starters N=0,000 n (%) | 2017 starters N=0,000 n (%) |
|---|--|--|--|--|--|--|
| Age (years) | | | | | | |
| <15 | 154 (6) | 175 (6) | 136 (6) | | | |
| 15-<25 | 1,520 (55) | 1,617 (55) | 1,310 (56) | | | |
| 25-<35 | 866 (31) | 907 (31) | 709 (30) | | | |
| 35-<45 | 208 (8) | 209 (7) | 176 (8) | | | |
| 45-<55 | 11 (<0.5) | 14 (<0.5) | 10 (<0.5) | | | |
| ≥55 | 1 (<0.5) | 1 (<0.5) | 0 (0) | | | |
| mean ± SD | 23 ± 7 | 23 ± 7 | 23 ± 7 | | | |
| median (IQR) | 22 (17-28) | 22 (17-28) | 22 (17-28) | | | |
| Database history before index date (years) | | | | | | |
| 1-<2 | 171 (6) | 219 (7) | 163 (7) | | | |
| 2-4 | 248 (9) | 223 (8) | 179 (8) | | | |
| >4 | 2,341 (84) | 2,481 (85) | 1,999 (85) | | | |
| mean ± SD | 11 ± 6 | 12 ± 6 | 12 ± 7 | | | |
| median (IQR) | 12 (6-16) | 12 (6-16) | 13 (7-17) | | | |
| Follow-up after index date (months)* | | | | | | |
| <6 | 1,316 (48) | 1,351 (46) | 1,108 (47) | | | |
| 6-12 | 1,444 (52) | 1,572 (54) | 1,233 (53) | | | |
| mean ± SD | 6 ± 4 | 6 ± 4 | 6 ± 4 | | | |
| median (IQR) | 6 (3-9) | 6 (3-9) | 6 (3-9) | | | |

* by definition, the follow-up will not be longer than 12 months (see section 9.2).

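### Concomitant use is given as a crude yearly percentage over 0 to 12 months of follow-up, so it is not a risk over any stated period; in PHARMO the age mix may also distort the trend

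*Protocol*

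**What the plan says.** Section 9.2 ends follow-up at transfer out of the database or at the end of the study period. It adds: "In the analysis by calendar year the end of the study period will be defined as December 31 of the year of index date". The extension follows the same scheme: "For the 2017 study extension an analysis by calendar years will be performed". The footnote to Table 15.1 confirms the ceiling: "by definition, the follow-up will not be longer than 12 months (see section 9.2").

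Section 9.3 assesses concomitant use from index to the end of follow-up, with contraceptive episodes built from one year before index. Section 9.7 sets the summary measure: "Categorical data will be presented as counts (n) and proportions". Tables 15.4 to 15.6 apply it per index year to four classes of use (plus a row for women with both concomitant and potential use) and to duration classes of up to 28, over 28 to 84, and over 84 days.

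Section 9.3.2 labels overlap as potential when the switch falls in the last prescription of an episode, and as concomitant when it comes before that prescription.

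Section 8.2 gives the purpose of the extension: "to assess trends in concomitant use over 2011-2017 (excluding 2013"). No fixed window, person-time, cumulative proportion or age adjustment of concomitant use is described, and Section 9.9 does not list the year-end cut as a limitation.

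**The concern.** A woman who starts in January can be observed for almost 12 months, one who starts in December for less than one. Both count equally in the denominator. Three things follow.

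- **Level.** Overlap that would arise after 31 December is missed, so the percentage has no stated time horizon.
- **Classification.** If the next refill falls after 31 December, a prescription looks like the last of its episode only because observation stopped. Use that would have been concomitant is then labelled potential. Late starters also cannot reach the class of over 84 days if overlap days are counted only to the end of follow-up, as the footnote on CPA/EE duration in Tables 15.4 to 15.6 implies.
- **Trend.** A crude percentage can move between years because the women differ in age or follow-up, with no change in prescribing to comparable women. The extension exists to report that trend to the regulator.

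**Working it through.** **1. The follow-up figures reproduce.** Women with under 6 months of follow-up in 2011, 2012 and 2014:

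- PHARMO (Table 15.1): "3,877 (49) | 3,573 (47) | 641 (46"), of 7,876, 7,562 and 1,401.
- THIN (Table 15.2): "1,316 (48) | 1,351 (46) | 1,108 (47"), of 2,760, 2,923 and 2,341.
- HSD (Table 15.3): 232 (47%), 224 (50%) and 118 (45%), of 495, 446 and 261.

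In all nine cohorts the two follow-up classes add up to N. Pooled, 12,440/26,065 = 47.7%. Start dates spread evenly over a year with a 31 December cut predict 50% under 6 months and a mean of 6 months, so the tables fit that model.

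**2. Understatement of a 12-month risk.** The protocol gives no rate or timing of overlap (the concomitant-use shells are empty), so these are assumptions, with follow-up uniform on 0 to 12 months.

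*Overlap arises after index at constant hazard.* With 12-month risk R and L = -ln(1-R), the expected crude proportion is 1 - (1-exp(-L))/L.

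| R | Crude | R / crude |
|---|---|---|
| 5% | 2.52% | 1.98 |
| 10% | 5.09% | 1.96 |
| 20% | 10.37% | 1.93 |
| 40% | 21.70% | 1.84 |

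*Overlap arises evenly within the first T months.* The share captured is 1 - T/24. The factor 1/(1 - T/24) is 1.33 for T = 6, 1.14 for T = 3 and 1.04 for T = 1.

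*Overlap present at index.* All at index gives 1.00. Half at index and half spread evenly over 12 months gives 1/(0.5 + 0.5 × 0.5) = 1.33.

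**3. Late starters.** Women starting after 8 October have under 84 days to 31 December. With even start dates that is about 84/365 = 23%.

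**4. Follow-up and the trend.** The PHARMO row in Table 15.1 reads "median (IQR) | 6 (3-9) | 6 (3-9) | 6 (3-9") for 2011, 2012 and 2014. The tabulated mean is 6 months in all nine cohorts. With class midpoints of 3 and 9 months, mean follow-up moves from 2011 to 2014 as follows:

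- PHARMO: 6.05 to 6.25 months (+3.4%)
- THIN: 6.14 to 6.16 (+0.3%)
- HSD: 6.19 to 6.29 (+1.6%)

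The PHARMO shift is detectable in so large a cohort (chi-square over three years, p about 0.01) but small. At a 12-month risk of 10% with constant hazard, moving the share under 6 months from 49% to 46% takes the crude figure from 5.14% to 5.29%.

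**5. Age and the trend.** Share under 25, 2011 to 2014:

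- PHARMO: (278+3,986)/7,876 = 54.1% to (13+482)/1,401 = 35.3%
- THIN: (154+1,520)/2,760 = 60.7% to (136+1,310)/2,341 = 61.8%
- HSD: (5+207)/495 = 42.8% to (1+105)/261 = 40.6%

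Suppose, purely for illustration, that concomitant use is 5% under 25 and 10% from 25 up, unchanged over time. The PHARMO crude figure is 0.541 × 5 + 0.459 × 10 = 7.3% in 2011 and 0.353 × 5 + 0.647 × 10 = 8.2% in 2014. With the risks reversed it goes from 7.7% to 6.8%. With 10% under 25 and 5% above, THIN moves only from 8.03% to 8.09% and HSD from 7.14% to 7.03%.

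**The case against.** The plan is descriptive. It claims no 12-month risk, footnotes the 12-month ceiling, and tabulates follow-up and age by year. For a utilisation study, the crude share among actual users is a legitimate quantity. Table 5.1 (amendment 6) also records that the regulator asked for the same methodology and mode of presentation as in the earlier study. All of this stands: it rules out replacing the crude rows, and it means the crude figure is hard to interpret rather than wrong.

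A reader might infer that the crude figure halves the true risk. The documents do not support that. A factor of 2 needs all overlap to arise after index at a constant rate for 12 months. Contraceptive episodes are traced from a year before index, so carry-over at index is captured whatever the start month. Overlap also needs ongoing CPA/EE use under a no-gap rule, which may favour early overlap.

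A reader might also infer that differing follow-up drives the trend. The same cut applies every year and the distributions for 2011, 2012 and 2014 are nearly identical, so truncation largely cancels there. Nor does age confounding extend to all three databases: THIN and HSD show no comparable shift.

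These methods could be left to a statistical analysis plan, which is not shown. But the cut-off, the summary measure and the table shells are fixed in the protocol itself.

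**Conclusion.** The point holds in limited form.

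- **Level:** the yearly percentage is not a risk over a stated period. Relative to a 12-month risk it is too low by a factor between 1 and about 2. That range assumes even start dates, no transfer-out, and overlap that does not cluster late in the year.
- **Classification:** the year-end cut can shift use from concomitant to potential, and it closes the class of over 84 days to roughly 23% of starters. How often relabelling occurs cannot be computed from the protocol.
- **Trend, follow-up:** no material distortion appears between 2011 and 2014. For 2015 to 2017 it is a possibility only.
- **Trend, age:** a possible distortion in PHARMO alone, where under-25s fell by 18.8 points across the 2013 change that the trend is meant to span. Its size and direction depend on age-specific rates that the protocol does not give.

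This calls for a cheap addition, not a redesign.

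**What to change.** Keep every crude row of Tables 15.4 to 15.6. For each database and year, add:

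1. The Kaplan-Meier cumulative proportion with first overlap of any kind (concomitant or potential combined) by 3 and 6 months after index, with 95% confidence intervals. Count overlap present at index at time 0 and censor at 31 December or transfer-out. Combining the two kinds matters: Kaplan-Meier estimates of each separately would still depend on which prescription looks last at year end.
2. The split into concomitant and potential use as a secondary result, with a note on the year-end relabelling.
3. The 6-month figure standardised to that database's 2011-2012 age distribution. This matters mainly for PHARMO. Sparse bands need merging (HSD 2014 has one woman under 15).

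Read the trend from the crude and the added rows together, and name the year-end cut among the limitations in Section 9.9.

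The cost is extra programming on dates and ages that the study already derives, a few more rows, and a second figure beside the crude one that needs explaining. HSD intervals will be wide: only 143 of its 261 starters in 2014 fall in the 6 to 12 month follow-up class.
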